### **2.3.2.3 Undetermined Stroke**

Undetermined stroke is defined as a stroke with insufficient information to allow categorization as A or B.

### **2.3.3 Examination**

**Outpatient (in clinic) or Inpatient (in hospital) physical neuro-examination at day 14, 30, 60, 90, 120, 150 and 180**

### **2.3.4 Stroke Disability**

Stroke disability should be measured by a reliable and valid scale in all cases, modified Rankin Scale (mRS) and NIHSS at day 14, 30, 60, 90, 120, 150 and 180 (see appendix 13.1 and 13.2)

## **2.4 Atrial Fibrillation Review Committee**

The Atrial Fibrillation Adjudication Committee will provide Atrial Fibrillation Classifications and Diagnosis prior to randomization on subjects with new onset atrial fibrillation if the local PI is in doubt of diagnosis. All patients will be reviewed by the Atrial Fibrillation Review Committee at the end of the study.

### **2.4.2 Atrial Fibrillation Classifications and Diagnosis **

#### **2.4.2.1 Definition**

- a. **Non Valvular Atrial fibrillation (NVAf)** is defined as a supraventricular tachyarrhythmia with rapid, uncoordinated atrial electrical activity and irregular ventricular responses in the presence of intact atrioventricular (AV) conduction. ECG, Holter, telemetry, or event monitor characteristics include:

1) irregular R-R intervals (when AV conduction is present), 2) absence of distinct repeating P waves, and 3) irregular atrial activity.

- b. **Premature atrial contractions (PACs)** with underlying sinus rhythm or organized atrial supraventricular tachyarrhythmias such as atrial tachycardia or atrial flutter will not constitute a diagnosis of AF

#### **2.4.2.2 Classification**

- a. **Paroxysmal** – Atrial fibrillation that terminates spontaneously or with intervention within seven days of onset. Episodes may recur with variable frequency.
- b. **Persistent** – Atrial fibrillation that is sustained for more than 7 days. Episodes often require pharmacologic or electrical cardioversion to restore sinus rhythm.
- c. **Long-standing persistent** – Atrial fibrillation that has lasted for more than 12 months.
- d. **Permanent** – Persistent atrial fibrillation where a joint decision by the patient and clinician has been made to no longer pursue a rhythm control strategy.
- e. **Non valvular Atrial fibrillation** – AF in the absence of rheumatic mitral stenosis, a mechanical valve

#### **2.4.2.3 Atrial Fibrillation Diagnosis**

- a. Known past medical history of atrial fibrillation (as documented in patient's medical record)
- b. Newly diagnosed atrial fibrillation lasting at least 10 seconds as documented by 12-lead electrocardiogram, rhythm strip, telemetry monitoring, Holter/event recorder monitoring.
- c. Pacemaker/ICD/implantable loop recorder interrogation – Electrograms must be used to make the diagnosis (marker channels and mode switch episodes are not sufficient or appropriate). Electrograms should be reviewed by a member of the Atrial Fibrillation Adjudication Committee

### **3 STUDY OBJECTIVES**

#### **3.1 Research Hypothesis**

Early anticoagulation treatment regimen with Apixaban at 0-3 days after TIA, 3-5 days after small ischemic stroke and 7 to 9days after medium ischemic stroke for patients with atrial fibrillation will result in a decreased incidence for recurrent ischemic stroke and without significant increase in risk of intracranial hemorrhage compared to conventional treatment for TIA, small and medium sized strokes.

#### **3.2 Primary Objective**

In patients with atrial fibrillation with recent cerebral ischemic symptoms (0-48 hours), to evaluate whether the treatment regimen with Apixaban (Three subgroups: TIA: day 0-3; small stroke: day 3-5; medium stroke: day 7-9) compared with standard of care treatment regimen with warfarin (Three subgroups: TIA: day 7±5; Small or medium stroke: day 14±5) reduces the composite endpoint of fatal stroke, recurrent ischemic stroke or TIA at 30 and 180 days. (See figure 1)

#### **3.3 Secondary Objectives**

In patients with atrial fibrillation with recent cerebral ischemic symptoms (0-48 hours), to evaluate whether the treatment regimen of early Apixaban (Three subgroups: TIA: day 0-3; small stroke: day 3-5; medium stroke: day 7-9) compared with standard of care treatment with warfarin (three subgroups: TIA: day 7±5; Small or medium stroke: day 14±5) does not increase the number of intracranial hemorrhage assessed by MRI/CT by 30 and 180 days.

Additional information will be collected on:

- Quality of Life
- Modified Rankin Score
- NIH Stroke Scale
- Echocardiography
- AF Burden (Event Monitor data).

#### 4 INVESTIGATIONAL PLAN

##### 4.1 General Schema of Study Design

This will be a multi-center, open label, randomized, active control, parallel-group pilot trial to examine the effect of initiation of APIXABAN at days 0-3 (TIA), days 3-5 (small stroke) and days 7-9 (medium stroke) to decrease fatal and/or recurrent stroke/TIA in 120 subjects who have suffered a recent (0 to 48 hours from symptoms) TIA, or small to medium ischemic stroke as defined by appendix 13.1 compared to standard of care warfarin treatment regimen. Subjects will be randomly assigned in a 1:1 ratio to one of two treatment arms (apixaban or warfarin). Subjects will be followed for a total of 180 days from screening through follow-up.

[figure not shown]

Figure 1

#### **4.1.1 Screening Phase**

Potential subjects will be screened using the protocol inclusion and exclusion criteria. All subjects will have a diagnosis of NVAf with TIA or small to moderate embolic stroke.

Subject consent will be obtained prior to any study related procedures being performed, including discontinuation of current therapy. All females of child bearing age will have a urine pregnancy test. Labs to assess liver and kidney function and an EKG will be obtained from the patients' hospital record or obtained at screening if not available at time of consent. A physical exam will be obtained at screening and at various points throughout the study.

The screening and baseline/randomization visit may be combined as long as all inclusion/exclusion criteria have been met prior to randomization. Otherwise, if these reports are not available at the time of screening then randomization and study initiation can be combined into one visit.

## **4.2 Study Duration, Enrollment and Number of Sites**

### **4.2.1 Duration of Study**

The study duration per subject will be approximately 180 days. The active treatment phase is dependent on the dosing category (TIA, small or medium ischemic stroke) that the subject is placed in and which treatment regimen the patient is randomized into.

### **4.2.2 Total Number of Study Sites/Total Number of Subjects Projected**

The study will be conducted at University of South Florida (USF Health's South Center for Advanced Health Care, USF Health's Morsani Center for Advance Health Care , Tampa General Hospital), University of Louisville (hospital and clinic), University of California Los Angeles (hospital and clinic), and Bayfront Cardiovascular Sciences for a total of 4 enrolling sites.

Recruitment will stop when approximately 120 subjects meeting eligibility criteria are enrolled. To account for drop-outs as well as screen-failures up to 125 subjects will be consented and randomized.

## **4.3 Study Population**

Adult patients with the diagnosis of atrial fibrillation and recent TIA or ischemic small to medium stroke . Recent TIA will be defined as up to 3 days from signs and symptoms, recent small stroke will be up to 5 days from signs and symptoms and recent medium stroke will up to 9 days from signs and symptoms.

### **4.3.1 Inclusion Criteria**

1. Signed Written Informed Consent
  - Before any study procedures are performed, subjects will have the details of the study described to them, and they will be given a written informed consent document to read. Then, if subjects consent to participate in the study, they will indicate that consent by signing and dating the informed consent document in the presence of study personnel.

2. Males and Females 18 years of age and over.
3. History of Nonvalvular Atrial Fibrillation (NVAf) by documentation in the medical history or newly diagnosed nonvalvular Atrial Fibrillation at time of study randomization by ECG, device or telemetry (see section 2.4.2)
4. Diagnosis of a recent TIA or small or medium ischemic stroke . Recent TIA is defined as up to 3 days from signs and symptoms, recent small stroke will be up to 5 days from signs and symptoms and recent medium stroke will up to 9 days from signs and symptoms. (See section 2.3.2)
5. Women of child-bearing potential must use a reliable method of contraception and must provide a negative pregnancy test at entry into the study and within 24 hours of study treatment initiation.
6. WOCBP must agree to follow instructions for method(s) of contraception for the duration of treatment with study drug Apixaban plus 5 half-lives (approximately 3 days) plus 30 days (duration of ovulatory cycle) for a total of 33 days post-treatment completion.
7. Males who are sexually active with WOCBP must agree to follow instructions for method(s) of contraception for the duration of treatment with Apixaban plus 5 half-lives (approximately 3 days) plus 90 days (duration of sperm turnover) for a total of 93 days post-treatment completion.
8. Azoospermic males and WOCBP who are continuously not heterosexually active are exempt from contraceptive requirements. However they must still undergo pregnancy testing as described in this section.

Investigators shall counsel WOCBP and male subjects who are sexually active with WOCBP on the importance of pregnancy prevention and the implications of an unexpected pregnancy. Investigators shall advise WOCBP and male subjects who are sexually active with WOCBP on the use of highly effective methods of contraception. Highly effective methods of contraception have a failure rate of < 1% when used consistently and correctly.

At a minimum, subjects must agree to the use of one method of highly effective contraception as listed below:

#### **HIGHLY EFFECTIVE METHODS OF CONTRACEPTION**

- Male condoms with spermicide
- Hormonal methods of contraception including combined oral contraceptive pills, vaginal ring, injectables, implants and intrauterine devices (IUDs) such as Mirena® by WOCBP subject or male subject's WOCBP partner. Female partners of male subjects participating in the study may use hormone based contraceptives as one of the acceptable methods of contraception since they will not be receiving study drug
- IUDs, such as ParaGard™
- Tubal ligation
- Vasectomy.
- Complete Abstinence\*

\*Complete abstinence is defined as complete avoidance of heterosexual intercourse and is an acceptable form of contraception for all study drugs. Female subjects must continue to have pregnancy tests. Acceptable alternate methods of highly effective contraception must be discussed in the event that the subject chooses to forego complete abstinence

#### 4.3.2 Exclusion Criteria

1. Hemorrhagic stroke
2. Large ischemic stroke
3. History of major bleeding within the last 6 months from time of subject enrollment (e.g. GI bleed).
4. History of intracranial bleed
  - a. Traumatic intracranial bleed within one year of randomization. (Traumatic ICH greater than one year of randomization is not an exclusion).
5. Current or history of bleeding disorders (e.g. blood dyscrasias)
6. Blood Pressure of 180/100 mmHg on hypertensive therapy day of randomization per PI discretion.
7. Current illicit drug use and/or chronic alcohol use per PI discretion.
8. Severe liver disease (AST/ALT 2x upper limit).
9. Patients with kidney disease meeting criteria to take 2.5 mg twice daily who are taking strong dual inhibitors of CYP3A4 and P-glycoprotein (e.g. ketoconazole, itraconazole, ritonavir, clarithromycin) .
10. Any other suspected etiology for stroke (e.g. ipsilateral carotid disease).
11. Greater than 3 Cerebral Micro-bleeds (CMB) on gradient recovery echo (GRE) or evidence of intracranial hemorrhage on CT at time of randomization. (SWI sequencing may be used if GRE sequencing is not obtainable)
12. Therapeutically anti-coagulated at time of admission (INR at admission greater than 2.0 on warfarin or took two consecutive doses of NOAC).
13. Absolute indication for use of warfarin only.( e.g. Mechanical Valve)
14. Absolute indication for anticoagulation prior to randomization window. (e.g. DVT)
15. Hemoglobin less than 9 gm/dl and/or platelet count less than 100 K/uL.
16. Requires dual antiplatelet therapy.

17. Daily use of NSAIDS
18. Pregnancy or lactation.
19. Any use of an investigational product within the past 30 days.
20. Prisoners or subjects who are involuntarily incarcerated.
21. Subjects who are compulsorily detained for treatment of either a psychiatric or physical (eg, infectious disease) illness.
22. Concurrent participation in another clinical study where use of an investigational product is used

Subjects that do not meet all of the enrollment criteria may not be enrolled. Any violations of these criteria will be reported in accordance with IRB Policies and Procedures.

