### 1.3 Name and Description of Investigational Product or Description of Intervention

Apixaban, a factor Xa (FXa) inhibitor, is chemically described as 1-(4-methoxyphenyl)-7-oxo-6-[4-(2-oxopiperidin-1-yl)phenyl]-4,5,6,7-tetrahydro-1H-pyrazolo[3,4-c]pyridine-3-carboxamide. Its molecular formula is C25H25N5O4, which corresponds to a molecular weight of 459.5. Apixaban has the following structural formula:

Apixaban is a white to pale-yellow powder. At physiological pH (1.2–6.8), apixaban does not ionize; its aqueous solubility across the physiological pH range is ~0.04 mg/mL.

This study is an open label, randomized, active controlled pilot study of Apixaban in subjects with NVAf who have, within 48 hours from signs and symptoms, been diagnosed with a TIA or a Small to Medium Ischemic Stroke as defined by the SACCO (see section 2.3).

In this study 120 patients with NVAf who have had a recent small or medium stroke or TIA (within 0-48 hours) will receive Apixaban twice a day for 180 days with drug initiation day 0-3 (TIA), day 3-5 (small stroke) or day 7-9 (medium stroke) respectively or receive standard of care warfarin starting at day 7±5 (TIA) or day 14 ±5 (small to medium ischemic stroke).

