## **1.4 Selection of Drugs and Dosages**

### **1.4.1 Apixaban**

The dosage of Apixaban is based on the clinical findings of studies in human subjects and its FDA approved dosage for patients with nonvalvular atrial fibrillation. Patients will receive 5mg dosage twice a day or 2.5 mg if they have any 2 of the following characteristics:

- age ≥80 years
- body weight ≤60 kg
- serum creatinine ≥1.5 mg/dL

Coadministration with CYP3A4 and P-glycoprotein inhibitors: For patients receiving Apixaban 5 mg twice daily when Apixaban is coadministered with drugs that are strong dual inhibitors of cytochrome P450 3A4 (CYP3A4) and P-glycoprotein (P-gp) (e.g., ketoconazole, itraconazole, ritonavir, clarithromycin), the recommended dose is 2.5 mg twice daily [ patients already taking 2.5 mg twice daily, coadministration of Apixaban with strong dual inhibitors of CYP3A4 and P- glycoprotein should be avoided .

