**5.2 Baseline Visit/Randomization**

The baseline/randomization visit will be performed up to 48 hours after signs and symptoms of stroke or TIA, and will be combined with the screening visit as long as all inclusion/exclusion criteria have met prior to randomization.

After subjects have been screened and enrolled in the study, baseline assessments will be performed. Patients will be stratified according to their type of stroke ( TIA, small or medium stroke) and randomized 1:1 in each group to ensure for equal number of subjects for each three types. Treatment with APIXABAN 5mg or 2.5mg based on clinical characteristics defined in section 1.4 or Warfarin ( target INR 2-3) will begin based on the randomization treatment regimen. Study treatment regimen is initiated based off of TIA or stroke size. Subjects in the Warfarin arm will return to clinic with unscheduled INR checks until they reached the standard INR of 2.0 to 3.0.

Hypertension will be treated per the AHA/ASA guidelines and are described below:

Goals for target blood pressure level or reduction from pretreatment baseline are uncertain and should be individualized, but it is reasonable to achieve a systolic pressure less than 140 mm Hg and a diastolic pressure less than 90 mm Hg. For patients with a recent lacunar stroke, it might be reasonable to target a systolic blood pressure of less than 130 mm Hg.

Resumption of Blood Pressure therapy is indicated for previously treated patients with hypertension.

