## 5.7 Subject Completion/Early Withdrawal

It will be documented whether or not each subject completed the clinical study. A subject is considered to have completed the study if he/she has taken all study medications for 6 months and has completed 6 month study assessments or withdrew from the study due to the occurrence of a recurrent embolic stroke, hemorrhagic transformation or death. If a subject does not complete the treatment phase, their data will be used for efficacy and for any safety analysis.

It is understood that withdrawals may occur during a trial. Each subject has the right to withdraw from the trial at any time for any reason without affecting the right to treatment by the investigator. Subjects who do not complete the treatment phase for other reasons then mentioned above, should be followed at day 14 and EOS visits, if possible. At minimum these patients should have a monthly phone call to assess AE/SAE and vital status if they are unable to continue follow-up in clinic.

Subjects needing to withdraw prior to the completion of the study and who do not agree to continue in follow-up should return to the clinic for completion of early withdrawal procedures, as outlined in table 1.

Reasons that a subject may discontinue the study include the following:

- Adverse events including recurrent stroke or hemorrhagic transformation
- Intercurrent illnesses
- Any significant new medical condition
- Protocol violation
- Non-compliance to study medication regimen

- Use of any investigational drug other than the study medication
- Intake of prohibited medication
- Pregnancy
- Subject withdrew consent or lost to follow-up
- Other (reason to be documented)

Withdrawals due to intercurrent illnesses or AEs will be fully documented in the CRF with the addition of supplementary information if available and/or appropriate. Withdrawals due to non-attendance will be followed-up by the investigator to obtain the reason for non-attendance.

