### 8.1.6 Randomization

Randomization of treatment was calculated in SAS 9.4 using a stratified, blocked PLAN procedure. For the 120 subjects to be randomized to either apixaban or warfarin, a random seed number was generated. Each subgroup of stroke type (small stroke, medium stroke and TIA) was randomized implementing block randomization using four blocks of 10. The treatment allocation was created by an unblinded statistician and given to the TGH research pharmacy. Blinded study envelopes are provided to study team members for randomization.

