### 9.3.2 Apixaban.

The dosage of Apixaban is based on the clinical findings of studies in human subjects and its FDA approved dosage for patients with non-valvular atrial fibrillation. Patients will receive 5mg dosage twice a day or 2.5 mg if they have any 2 of the following characteristics:

- age  $\geq 80$  years
- body weight  $\leq 60$  kg
- serum creatinine  $\geq 1.5$  mg/dL

Coadministration with CYP3A4 and P- glycoprotein inhibitors: For patients receiving Apixaban 5 mg twice daily when Apixaban is coadministered with drugs that are strong dual inhibitors of cytochrome P450 3A4 (CYP3A4) and P-glycoprotein (P-gp) (e.g., ketoconazole, itraconazole, ritonavir, clarithromycin), the recommended dose is 2.5 mg twice daily [ patients already taking 2.5 mg twice daily, coadministration of Apixaban with strongdual inhibitors of CYP3A4 and P- glycoprotein should be avoided

If a dose of Apixaban is not taken at the scheduled time, the dose should be taken as soon as possible on the same day and twice-daily administration should be resumed. The dose should not be doubled to make up for a missed dose.

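### Exclusion 9 is narrower than the apixaban dosing rule: strong dual inhibitor users who qualify for 2.5 mg on age and weight alone stay eligible

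*Combined protocol and SAP*

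**What the plan says.** Section 4.3.2, criterion 9, excludes "Patients with kidney disease meeting criteria to take 2.5 mg twice daily who are taking strong dual inhibitors of CYP3A4 and P-glycoprotein". No other exclusion criterion names these drugs.

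Section 1.4.1 sets the dose: "Patients will receive 5mg dosage twice a day or 2.5 mg if they have any 2 of the following characteristics". The three characteristics are age ≥80 years, body weight ≤60 kg and serum creatinine ≥1.5 mg/dL. It then treats strong dual inhibitors in two ways. A patient on 5 mg who takes one is reduced to 2.5 mg. For "patients already taking 2.5 mg twice daily, coadministration of Apixaban with strong dual inhibitors of CYP3A4 and P- glycoprotein should be avoided". Section 9.3.2 repeats both rules. Neither section makes the advice to avoid the combination depend on kidney disease.

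Two other places bear on the point. Section 5.7 gives "Intake of prohibited medication" as a reason to discontinue but lists no drugs. Section 5.8 lets subjects stay on their existing medicines and does not mention these inhibitors.

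**The concern.** The entry criterion and the dosing rule address the same drug interaction but cover different patients. Someone who qualifies for 2.5 mg on age and weight, has no kidney disease and takes a strong dual inhibitor can be randomised, although sections 1.4.1 and 9.3.2 say the combination should be avoided at that dose.

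If that patient is assigned to apixaban, the site has to stop the inhibitor, withhold apixaban or go against the advice in 9.3.2. Withholding the assigned drug could also take the patient out of the per-protocol analysis described in section 8.1.4. Settling the question before randomisation avoids all of this. What is at stake is bleeding safety in a rare patient and a tidy entry rule, not the trial's statistical properties.

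**Working it through.** **Which patients the two rules cover.** The protocol does not define kidney disease. I take it here to mean creatinine ≥1.5 mg/dL, the only renal item among the three characteristics.

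| Ways to meet any two of three | Inhibitor to be avoided (1.4.1, 9.3.2) | Excluded by criterion 9 |
|---|---|---|
| Age + creatinine | Yes | Yes |
| Weight + creatinine | Yes | Yes |
| Age + weight + creatinine | Yes | Yes |
| Age + weight only | Yes | **No** |

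Criterion 9 covers three of the four combinations. With the renal qualifier deleted it covers all four. Patients reduced from 5 mg to 2.5 mg only because of the inhibitor are permitted the combination and are not part of the gap.

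**Time between randomisation and first apixaban dose.** Section 5.2 states: "The baseline/randomization visit will be performed up to 48 hours after signs and symptoms of stroke or TIA". Randomisation therefore falls on day 0 to 2. The apixaban start windows are in Table 2 (section 5.3). The shortest interval is the earliest start minus day 2, and the longest is the latest start minus day 0.

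- TIA, start day 0–3: 0 to 3 days. The heading of section 6.3 allows drug initiation on the day of randomisation.
- Small stroke, start day 3–5: 3 − 2 = 1 day to 5 − 0 = 5 days.
- Medium stroke, start day 7–9: 7 − 2 = 5 days to 9 − 0 = 9 days.

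**How many patients.** Section 8.1.6 says: "Each subgroup of stroke type (small stroke, medium stroke and TIA) was randomized implementing block randomization using four blocks of 10". That gives 4 × 10 = 40 per stratum, and at 1:1 allocation 20 on apixaban per stratum and 60 in all.

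The documents report neither a weight distribution nor a rate of inhibitor use. Two ranges are therefore assumed:

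- share of patients with age ≥80 and weight ≤60 kg and no kidney disease: 0.02 to 0.10;
- share of those taking a strong dual inhibitor: 0.005 to 0.05.

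The probability per patient is p = 0.02 × 0.005 = 0.0001 at the low end and 0.10 × 0.05 = 0.005 at the high end. The expected number is n × p, and the chance of at least one such patient is 1 − (1 − p)^n.

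| Group | n | Expected number | Chance of at least one |
|---|---|---|---|
| All randomised | 120 | 0.012 to 0.60 | – |
| Apixaban arm | 60 | 0.006 to 0.30 | 0.6% to 26.0% |
| Apixaban, small and medium stroke | 40 | 0.004 to 0.20 | – |
| Apixaban, TIA | 20 | 0.002 to 0.10 | 0.2% to 9.5% |

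The upper figures need both assumptions at their maximum.

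**The case against.** The strongest reply is that the protocol already deals with the hazard where it arises. Sections 1.4.1 and 9.3.2 both say the combination should be avoided, whichever two characteristics apply, and nothing directs a site to give it. Weight, laboratory results and medicines are reviewed at Visit 1 (section 6.1), and medication changes are assessed again at drug initiation (section 6.3). This stands, and it is why the point is minor. It does not close the gap at entry, because the dosing rule operates only once apixaban has been assigned.

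A second reply is that a lack of time is avoidable even for TIA. A site randomising by day 2 may start as late as day 3, so it can make room by waiting. That is true, but the zero minimum is also real: same-day initiation is allowed, and a site that has not noticed the interaction has no reason to wait. Inclusion criterion 4 defines recent events as up to 3, 5 and 9 days from symptoms. A site enrolling on those limits rather than 48 hours could have no lead time in any stratum.

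Third, the dosing text is advisory and the patient counts rest on assumed rates. Both observations are fair. The counts show only that the group is tiny, and they cannot support more than that.

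Fourth, the reach of the criterion depends on the undefined term. A site taking a broad view of renal impairment would narrow the gap. One that requires a charted diagnosis would widen it, by also admitting an inhibitor user aged 80 or over with creatinine ≥1.5 mg/dL but no renal diagnosis. Removing the phrase disposes of both readings.

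Last, the edit would also exclude patients who would have drawn warfarin, to whom this rule does not apply, and some whose inhibitor could simply have been stopped. That is a genuine cost, though a very small one.

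**Conclusion.** The concern holds as a minor alignment of wording. Criterion 9 misses one of the four routes to the 2.5 mg dose, and no other entry criterion covers it. That the texts differ is certain. The practical reach is not, because it depends on how sites read kidney disease and on rates the documents do not give. On the assumed ranges, well under one patient is expected in the whole trial. The dosing rule in 9.3.2 is a real safeguard after assignment, and section 5.7 gives partial cover after entry. Sample size, power, endpoints and analysis are unaffected.

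**What to change.** In exclusion criterion 9, delete the three words that limit it to kidney disease, and after the reference to the 2.5 mg criteria add a parenthesis: any 2 of age ≥80, weight ≤60 kg, creatinine ≥1.5 mg/dL. The criterion then refers to the three-item rule itself, so patients reduced from 5 mg only because of an inhibitor remain eligible. Section 9.3.2 should continue to govern inhibitors started after randomisation, which an entry criterion cannot catch.

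The cost is one edited line and the possible loss of a very few otherwise eligible patients. No assessment is added, since weight, laboratory results and medicines are already reviewed at Visit 1. The criterion is applied before randomisation, so it affects both arms equally.
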